#### 6.7.5 Definition of Maximum Tolerated Dose

The MTD will be selected from all investigated dose levels that have not been previously declared to be unsafe with a dose unacceptable decision according to the mTPI-2 decision rules (see [Table 16](#)). With this constraint, the MTD will be determined as the dose level with the DLT estimate closest to the target toxicity level of 30%.

In the case of dose levels with estimated toxicity of equal distance (tied dose levels) from the target toxicity of 30%, the following approach will be used ([Ji et al, 2010](#)): among all tied dose levels the highest dose level with target toxicity  $\leq 30\%$  will be selected, unless all tied dose levels have estimated toxicity  $> 30\%$ , in which case the lowest dose level will be selected.

### 6.7.6 Definition of a DLT Evaluable Participant

A DLT evaluable participant is defined as a participant who receives [Ac]-FPI-2068 and either completes the DLT observation period without a DLT or experiences a DLT at any time during the DLT observation period. Participants who are unable to complete the 56-day DLT observation period, for reasons other than DLT (e.g., rapid disease progression or death) will be replaced; therefore, additional participants may be enrolled.

### 6.7.7 Definition of a DLT

The DLT observation period will be 56 days during the first cycle of therapeutic treatment, and subsequent cycles will be administered every 56 days.

The cycle length is set at 56 days in order to balance the need to monitor toxicities and associated resolution time with the need to re-treat participants with advanced disease. This duration is deemed appropriate based upon the rate of radioactive decay and expected biological clearance of [Ac]-FPI-2068 following administration to participants.

A DLT is defined by the occurrence of any of the toxicities listed below within the first cycle of treatment excluding toxicities clearly related to disease progression or intercurrent illness.

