### 2.3.1 Risk Assessment

**Table 5 Risk Assessment**

Potential risk of clinical significance	Mitigation strategy
[Ac]-FPI-2068 and [In]-FPI-2107]	
Bone marrow suppression leading to haematological toxicity	Eligibility criteria excludes participants with low haematological parameters and previous extensive radiotherapy to pelvis, dosimetry estimates preclude exceeding CSP defined absorbed dose limit (Table 12), haematology evaluations per SoAs, included in DLT criteria, and TMGs in place.
Hepatic disorders, liver function test abnormalities (e.g., raised ALT/AST)	Inclusion criteria excludes participants with abnormal hepatic parameters, dosimetry estimates preclude exceeding CSP defined absorbed dose limit (Table 12), regular clinical chemistry evaluations and ADA monitoring per SoAs, included in DLT criteria, and TMGs in place.
Lung toxicities (e.g., ILD/pneumonitis, radiation pneumonitis)	Investigator advised to monitor for signs and symptoms of ILD/pneumonitis throughout the course of the study. Inclusion criteria requires further evaluation of participants with a history of lung toxicities and excludes those with ongoing pulmonary dysfunction, dosimetry estimates preclude exceeding CSP-defined absorbed dose limits (Table 12), baseline CT scan and further imaging as clinically indicated, blood sample evaluations, ADA monitoring per SoAs, ILD markers as clinically indicated, and TMGs in place.
Renal disorders including renal failure	Inclusion criteria excludes participants with insufficient renal function, dosimetry estimates preclude exceeding CSP defined absorbed dose limit (Table 12), blood sample evaluations, ADA monitoring per SoAs, and TMGs in place.
Other on-target (EGFR, c-MET driven) non-critical organ toxicities such as in skin, eye	Physical examinations and clinical monitoring
ADA formation.	Blood sampling to check for ADA per SoAs and management of organ-specific toxicities detailed above.
Study procedures	
Infusion-related reactions	Participants will be closely monitored during administration of study intervention and for 30 minutes after administration, and TMGs in place.

ADA, anti-drug antibody; ALT, alanine aminotransferase; AST, aspartate aminotransferase; c-MET, mesenchymal-epithelial transition factor; CT, computed tomography; DLT, dose-limiting toxicity; EGFR, epidermal growth factor receptor; ILD, interstitial lung disease; SoA, schedule of activities; TMG, toxicity management guidelines.

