Prior to the administration of [Ac]-FPI-2068, all AEs related to [In]-FPI-2107 or FPI-2053 should be resolved to Grade 1 or baseline. A delay of 28 days is acceptable from the time of the last [In]-FPI-2107 ( $\pm$  FPI-2053) administration to the administration of [Ac]-FPI-2068 if an AE related to [In]-FPI-2107 or FPI-2053 requires longer time for resolution. In circumstances (e.g., intercurrent illness, etc.) where a delay of [Ac]-FPI-2068 administration may be necessary, the Sponsor and/or Medical Monitor must be consulted to discuss whether the participant can receive [Ac]-FPI-2068. In this scenario, Sponsor and/or Medical Monitor agreement is required prior to [Ac]-FPI-2068 administration. Laboratory results confirming bone marrow and organ function, within retreatment criteria requirements must be documented within 48 hours prior to each cycle of [Ac]-FPI-2068 administration.

Refer to Sections 8.1.4 through 8.1.7 for the assessment details and timepoints performed, and for the biospecimens and information collected during the Treatment Period.

4. *End of Treatment and 28- or 42-Day (+ 14 days) Safety Follow-Up Period:* Participants who do not receive any [Ac]-FPI-2068 (i.e., those who do not enter the Treatment Period) will have a Day 28 ( $\pm$  3 days) safety visit as their last study visit. Participants who receive treatment with [Ac]-FPI-2068 will have a safety visit on Day 42 (+ 14 days) before entering the Extended Safety Follow-up Period.
5. *Extended Safety Follow-up Period:* Because cumulative radiation exposure may be associated with an increased risk of delayed onset of radiation-induced toxicity, participants will undergo additional safety assessments at 3-month intervals. The Extended Safety Follow-up Period will begin 3 months following the last dose of

[Ac]-FPI-2068, and will continue every 3 months for 2 years, then every 6 months for an additional 3 years up to 5 years, or until the participant withdraws from the study (see Section 7.2). Refer to Section 8.1.8 for the assessment details and timepoints performed, and for the biospecimens and information collected during the Extended Safety Follow-up Period.

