AUC, area under the curve; AUCcyno, area under the curve in cynomolgus monkey; AUCh, area under the curve in human; Cmax, maximum concentration after dosing; Cmax, cyno, maximum concentration after dosing in cynomolgus monkey; Cmax, h, maximum concentration after dosing in human; Cmax, lower, maximum concentration after dosing lower limit; Cmax, upper, maximum concentration after dosing upper limit; GLP, Good Laboratory Practice. PK, pharmacokinetics.

a Margins calculated based on upper limit of mass dose range

Mass dose range of [Ac]-FPI-2068 based on manufacturing target specific activity range of 0.814-3.145 MBq/mg and a 10-day shelf-life. AUC and Cmax of FPI-2054 from cynomolgus monkey based on Day 1 PK profiles from a 5 week GLP toxicology Study 1589.04 (IV bolus).

Prior to treatment with [Ac]-FPI-2068, participants will be imaged with [In]-FPI-2107 (with and/or without predose administration of FPI-2053) to determine participant eligibility per local review. Prior to the administration of [Ac]-FPI-2068, individual dosimetry assessments and tumour-to-background-ratio (TBR) will be conducted centrally and reviewed with the Investigator to confirm eligibility and estimate the maximum allowable cycles of [Ac]-FPI-2068. All subsequent cycles of [Ac]-FPI-2068 will be based on assigned dose level and individual dosimetry such that an individual participant's cumulative radiation absorbed dose will not exceed limits of 23 Gy for kidneys, 31 Gy for liver, 16.5 Gy for lungs, and for Part A only, 2 Gy for red bone marrow. If a participant reaches a cycle in which the planned administered dose exceeds prespecified individualised cumulative radiation dose limits, the participant may receive a reduced administration such that the specified cumulative limit is not reached.

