### **6.7.3 [Ac]-FPI-2068**

For a participant to be eligible to receive repeat dosing with [Ac]-FPI-2068, they must meet the retreatment criteria defined in [Table 15](#) within 56 days (+ 4 weeks) from their previous [Ac]-FPI-2068 administration. If retreatment criteria are not met, the treatment administration may be held for up to 28 days. If treatment-related toxicities are not resolved within this window, then the participant will discontinue study treatment. Adjustments to these guidelines may occur if agreed by the Investigator, Sponsor, and Medical Monitor.

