Tumour biopsy (if applicable)				Day 8 to Day 11 f				8.8.2.1	
PK samples	Table 26							8.7.1	
ADA samples	Table 26							8.7.2	

ADA, anti-drug antibody; AE, adverse event; bsAb, bispecific monovalent antibody; CT, computed tomography; ctDNA, circulating tumour DNA; D, day; ECG, electrocardiogram; ECOG, Eastern Cooperative Oncology Group; FDG, fluorodeoxyglucose; inj., injection; MRI, magnetic resonance imaging; PET, positron emission tomography; PK, pharmacokinetics; RECIST, Response Evaluation Criteria in Solid Tumours; RNA, ribonucleic acid; TCR, T-cell receptor; TEAE, treatment-emergent adverse event.

a If clinically indicated, any procedure or assessment may be done as an unscheduled visit.

b Each cycle must be at least 56 days duration.

c Obtain within 48 hours prior to the injection and confirm that all tests are within the eligibility requirements.

d AEs reported after [In]-FPI-2107 administration will be reported as TEAEs. All TEAEs related to [In]-FPI-2107 should be resolved to < Grade 1 or to baseline within 14-days post-[In]-FPI-2107 administration and prior to [Ac]-FPI-2068 administration.

e A consistent modality of scanning (CT, MRI) should be used for the participant throughout the course of the study. Participants who experience a PR should have their response confirmed 4-6 weeks following documentation of the initial response. CT scan or MRI of chest, abdomen, and pelvis (and other organs if medically indicated) can be obtained for those with non-avid FDG-PET/CT scan. Tumour assessment scans are only required at 2, 4, 6 months (±1 week) and then every 3 months (±2 weeks) until progression or start of new systemic anti-cancer treatment.

f If a tumour sample can be safely obtained, every effort should be made to collect a core biopsy between Day 8 and Day 11 in Cycle 1 or Cycle 2 of the Treatment Period.

### 8.1.5 Treatment Period - Part B (Hot Dose Escalation with Unlabelled bsAb) – Cycle 1

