### 8.1.8 End of Treatment and Extended Follow-up Period

**Table 25** Schedule of Assessments - End of Treatment and Extended Follow-up Period

Assessments/procedures a	End of Treatment b	42 -Day (+ 14 days) Safety Follow-Up c	Extended Safety Follow-up (after the last dose)	Details in Section/Appendix
	± 3 days	After the last dose (± 3 days)	Every 3 months (± 2 weeks) for 2 years then every 6 months for 3 years	
Subsequent anti-cancer treatment	X	X	X	9.4.2
AE monitoring	X	X	X d	8.5
Concomitant medications and procedures	X	X		6.6
Haematology (whole blood) with blood smear (pathology)	X	X	X	8.4.4
Clinical chemistry (serum or plasma)	X	X	X	8.4.4
Thyroid panel		X		8.4.4
Urinalysis		X		8.4.4
Pregnancy test (blood or urine, in accordance with institutional practice)	X			8.4.4
Complete physical examination	X			8.4.1
Symptom-directed physical examination		X		8.4.1
ECOG Performance Status	X	X		8.4.5
Weight	X			8.4.1
Ophthalmologic examination	X			8.4.6.2
CT or MRI for RECIST 1.1 Response Assessments	X d		X e	8.2
Serum for tumour marker measurement (e.g., CA-19-9, CEA, etc.) g	X		X h	8.8.1.3
Blood for TCR analysis	X		X	8.8.1.1

ADA, anti-drug antibody; AE, adverse event; CA-19-9, carbohydrate antigen-19-9; CEA, carcinoembryonic antigen; CT, computed tomography; ctDNA, circulating tumour DNA; ECOG, Eastern Cooperative Oncology Group; MRI, magnetic resonance imaging; PK, pharmacokinetics; RECIST, Response Evaluation Criteria in Solid Tumours; RNA, ribonucleic acid; TCR, T-cell receptor.

**a** If clinically indicated, any procedure or assessment may be conducted as an unscheduled visit.

**b** The End of Treatment visit should be conducted within 7 days of the decision to permanently discontinue treatment with  $[^{225}\text{Ac}]$ -FPI-2068.

The Follow-up Visits should be scheduled within CSP-defined timeframe (e.g., 42-56 days) based on the date of the last dose of IMP.

d Only related AEs to be collected in the Extended Follow-Up Period.

Only related AEs to be collected in the Extended Follow Up Period.

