Visit/timepoint	PK	TriPLICATE 12-lead ECG a	Blood for RNA and TCR analysis	Plasma for ctDNA analysis	ADA samples
administration					
	1 hr post administration	± 10 min	X		
	2 h post administration	± 15 min	X		
	4 h post administration	± 30 min	X		
	8 h post administration b	± 30 min	X		
Day 8 (7 days [± 6 h] post injection)	During visit day	During visit day			X
Day 15 (14 days [± 2 days] post injection)	During visit day	During visit day	During visit day	During visit day	
Day 22 (21 days [± 2 days] post injection)	During visit day	During visit day			X
Day 29 (28 days [± 3 days] post injection)	During visit day	During visit day			
Day 57 (56 days [± 3 days] post injection, if Cycle 2 is delayed)	During visit day	During visit day	X c	X c	X c
Cycles 2 and beyond Treatment Period					
Day of [  Ac]-FPI-2068 administration	Predose FPI-2053 administration (within 2 h prior)	X	X	X	X
	End of FPI-2053 administration	+ 5 min	X		
	Predose [  Ac]-FPI-2068 administration	- 5 min	X		
	End of [  Ac]-FPI-2068	+ 5 min	X		

Visit/timepoint	PK	TriPLICATE 12-lead ECG a	BLOOD for RNA and TCR analysis	Plasma for ctDNA analysis	ADA samples
administration					
Day 15 (14 days [ $\pm$ 2 days] post injection)			During visit day	During visit day	
Day 57 (56 days [ $\pm$ 3 days] post injection, if next cycle is delayed)			X c	X c	X c

ADA, anti-drug antibody; bsAb, bispecific monovalent antibody; CT, computed tomography; ctDNA, circulating tumour DNA; ECG, electrocardiogram; PK, pharmacokinetics; RNA, ribonucleic acid; SPECT, single-photon emission computed tomography; TCR, T-cell receptor.

a ECG may be performed, if clinically indicated, at any other visit/timepoint. ECGs must be performed prior to collection of the PK sample at the same timepoint.

b Not required initially, but if early PK data indicates that it is necessary, the 8-hour PK timepoint will be collected.

c If 8 h post injection PK sample is drawn.

d The 28 or 42-day (+ 14 days) Safety Visit only occurs if the participant does not proceed to the treatment phase (i.e., only receives FPI-2053 and [In]-FPI-2107).

e Blood samples for RNA, ctDNA, and ADA assessments at End of Treatment taken only if participant does not progress to next cycle.

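### The DLT window is 56 days, but Cycle 1 safety counts stop at Day 36, so a symptom-free cytopenia that starts and recovers before about Day 55-57 can go uncounted as a DLT

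*Protocol*

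**What the plan says.** Section 6.7.7 fixes the window: "The DLT observation period will be 56 days during the first cycle of therapeutic treatment". Section 6.7.7.1 lists DLTs that can be met on blood counts alone: a platelet count in the Grade 4 range for any length of time, Grade 3 platelets for more than 7 days, and Grade 4 neutrophils for more than 7 days. Chemistry can also decide a DLT, through the Hy's Law combination and Grade 3 or higher non-haematologic toxicity.

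Tables 21, 22 and 23 place Cycle 1 haematology and chemistry before the Day 1 injection and on Days 8, 15, 22, 29 and 36 (±3). None has a later Cycle 1 column. What comes next depends on the participant:

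- **Cycle 2 on time.** Section 4.1.4: "Laboratory results confirming bone marrow and organ function, within retreatment criteria requirements must be documented within 48 hours prior to each cycle".
- **Stopped after Cycle 1.** Table 25 gives safety laboratories at End of Treatment and at one safety visit: "The Follow-up Visits should be scheduled within CSP-defined timeframe (e.g., 42-56 days) based on the date of the last dose of IMP".
- **Cycle 2 delayed.** Section 6.7.3: "If retreatment criteria are not met, the treatment administration may be held for up to 28 days". Tables 26-28 hold a visit at "Day 57 (56 days [± 3 days] post injection, if Cycle 2 is delayed"), but its columns are PK, ECG, RNA/TCR, ctDNA and ADA only.

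A general safeguard stands in footnote a of Table 21: "If clinically indicated, any procedure or assessment may be done as an unscheduled visit".

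**The concern.** The window and the measurements that fill it do not match. The DLT count is the only input to the Table 16 decision besides the number treated, and over the last third of the window a count-only DLT is looked for about once instead of weekly. An episode that comes and goes between draws enters Table 16 as no DLT. That error runs in one direction only, towards escalation. The Safety Review Committee cannot correct it, because it can review only counts that were drawn.

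The protocol relies on these counts. For marrow suppression, Table 5 lists among its mitigations "haematology evaluations per SoAs, included in DLT criteria, and TMGs in place". A further mitigation, the absorbed-dose limit for marrow, applies "for Part A only, 2 Gy for red bone marrow" (Section 4.3.3). Part B, where Table 16 is used, does not have it.

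**Working it through.** **1. The plan's own figure.** I rebuilt Table 16 from a beta-binomial model with a target of 30%, equivalence interval 25-35%, sub-intervals of width 0.10 and a 95% safety cut-off. The Beta(1,1) prior is my assumption. Every printed cell is reproduced except 0/1, 0/2, 1/1 and 1/2. There the calculation gives E, E, D and D, which are the values the footnotes say were changed to S. Table 16 is correct; the question is the count fed into it.

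**2. Spacing of scheduled counts.**
- Days 1, 8, 15, 22, 29, 36: 7 days apart.
- On-time Cycle 2 is Day 57, so the 48-hour draw falls on Day 55-57. Gap: 55 − 36 = 19 to 57 − 36 = 21 days.
- With Day 36 taken at Day 33-39: 55 − 39 = 16 to 57 − 33 = 24 days.
- Days without a scheduled count, taking the earliest draw: Days 37-54 = 18, and 18/56 = 32%.

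**3. What fits unseen.** The longest episode between two draws is the gap minus 1: 7 − 1 = 6 days up to Day 36, then 19 − 1 = 18 to 21 − 1 = 20 days. These are calendar ceilings. Illustration, assuming onset uniform over 56 days and no symptoms: an 8-day episode falls wholly inside the gap with probability (19 − 8)/56 = 0.20 to (21 − 8)/56 = 0.23.

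**4. Effect in Table 16 of one missed DLT.**

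| True count | Decision | Seen as | Decision |
|---|---|---|---|
| 1/3 | S | 0/3 | E |
| 1/4 | S | 0/4 | E |
| 2/5 | D | 1/5 | E |
| 2/6, 2/7, 2/8 | S | 1/6, 1/7, 1/8 | E |
| 3/9 | S | 2/9 | E |

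Illustration with an assumed miss rate, at a true DLT rate of 40%: the chance of seeing 0/3 is 0.60³ = 0.216 with none missed, (1 − 0.36)³ = 0.262 with 10% missed and (1 − 0.30)³ = 0.343 with 25% missed.

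**5. Participants who stop.** With the safety visit 42 days after dosing, 56 − 42 = 14 days of the window (25%) have no scheduled count after it, unless End of Treatment falls there.

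**6. With draws at Days 43 and 50.** Nominal gaps are 7, 7 and 5-7 days, so the longest unseen episode is 6 days. With ±2-day windows on the new draws, the widest gaps are 45 − 33 = 12, 52 − 41 = 11 and 57 − 48 = 9, so up to 11 days can go unseen, against 24 − 1 = 23 now. Days 29 and 36, both ±3, already allow 39 − 26 = 13. The late window would then be no sparser than the early one, but it would not be gap-free.

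**7. Febrile-neutropenia threshold.** The Grade 3 line pairs 38.3°C with 100.4°F for sustained fever. But 38.3 × 1.8 + 32 = 100.9°F, and (100.4 − 32)/1.8 = 38.0°C. The Grade 4 line has 38°C. As written, a sustained 38.0-38.2°C is a DLT in one unit and not in the other.

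**The case against.** The strongest reply is that the gap is narrow. A missed event must begin after five post-dose weekly counts, reach Grade 3 or 4 without symptoms, and recover by Day 55-57, since otherwise Table 15 forces a hold. AE monitoring is continuous, and a fall already visible at Day 36 would normally prompt an unscheduled test. Nothing in the protocol shows that such late, self-resolving cytopenia is common. All of this stands and limits the weight of the point. It does not close the gap, because an unscheduled test needs a clinical indication and a late symptom-free fall gives none.

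Three stronger readings are tempting and not supported:

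- **A 28-day hold leaves about seven weeks without counts.** A hold for failed retreatment criteria means counts were taken when Cycle 2 was due. The missing Day 57 laboratories matter mainly for other delays, such as intercurrent illness, where Section 4.1.4 asks for consultation with the sponsor or medical monitor.
- **Part B marrow doses make late cytopenia likely.** Scaling the Table 10 coefficients linearly for 70 kg (an assumption) to 25, 40 and 70 kBq/kg gives 1.15, 1.84 and 3.22 Sv per cycle with saturating predose (657 mSv/MBq), but 0.53, 0.85 and 1.48 Sv without predose (303 mSv/MBq). The table's limit is 2. Neither set says when counts would fall.
- **Two more draws would catch every episode over 7 days and establish its length.** The first holds only on nominal days. The second needs a repeat count, since one value cannot show duration.

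The differing AE collection rules for extended follow-up in Section 8.5.1 and Table 25 lie outside the DLT window and are a separate matter.

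**Conclusion.** The mismatch is real and appears in all three Cycle 1 schedules. For an on-time participant, a count-only DLT that starts after Day 36 without symptoms and recovers before about Day 55-57 can be missed, and each one missed moves Table 16 towards escalation. The spacing and the Table 16 changes follow directly from the protocol. The frequency does not: the 0.20-0.23 and the 0/3 probabilities rest on assumed uniform onset and assumed miss rates, and they are illustrations only. A change is advisable because it is cheap and concerns safety; the present schedule does not make the escalation rule invalid. The temperature in the Grade 3 febrile-neutropenia line is a plain internal contradiction and should be corrected regardless.

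**What to change.** 1. Add local haematology and chemistry at about Days 43 and 50 to Tables 21-23, with stated windows (for example ±1-2 days). Put the same draws in Table 25 for participants who stop after Cycle 1 while still inside the 56 days. Section 8.1 moves them to that schedule, so columns in Tables 21-23 alone would not bind them.
2. Require a repeat count when a platelet value of Grade 3 or worse, or a Grade 4 neutrophil value, is seen, so that duration beyond 7 days can be judged.
3. Add haematology and chemistry to the existing Day 57 visit when Cycle 2 is delayed.
4. Change the Grade 3 sustained temperature to ≥ 38°C (100.4°F).

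The evaluability rule in Section 6.7.6 stays as it is, so nobody becomes a replacement because of the new draws.

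Cost: two short local laboratory visits per participant in Cycle 1, 2 × (9 + 18) = 54 draws in Parts A and B, or 2 × (9 + 18 + 20 + 60) = 214 if backfill and RP2D participants follow the same tables. Repeat counts come on top. This adds visits to a protocol whose current version removed Day 2 and Day 3 sampling to reduce burden, and the amendment needs ethics and regulatory approval.
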